9.2 Endpoints

- Adaptive speech in noise [signal-to-noise ratio, 50% speech understanding]
- Preference of device. Only Baha 6 Max SP and Baha 5 SP.
- Diary. Only Baha 6 Max SP and Baha 5 SP.
 - Daily use of sound processors (hours)
 - Change of battery
 - Switch to their own sound processor and the reason for change
- Thresholds audiology, sound-field [0.25, 0.5, 1.0, 2.0, 3.0, 4.0, 6.0, 8.0 9.0 and 10.0 kHz]
- Speech in quiet [% correctly perceived words at 65dB SPL]
- Evaluation of sound quality and listening effort through sound clips. Only Baha 6 Max SP and Baha 5 SP.

9.2.1 Primary Endpoints

- Primary endpoint for comparison between Baha 6 Max SP and unaided.
 - Adaptive speech in noise [signal-to-noise ratio, 50% speech understanding]
- Primary endpoint for comparison between Baha 6 Max SP and Baha 5 SP.
 - Preference of device.

9.2.2 Secondary Endpoints

- Daily use of sound processors (hours) from Diary, Only Baha 6 Max SP vs Baha 5 SP
- Change of battery from Diary, Only Baha 6 Max SP vs Baha 5 SP
- Switch to their own sound processor and the reason for change from Diary
- Only Baha 6 Max SP vs Baha 5 SP
- Adaptive speech in noise [signal-to-noise ratio, 50% speech understanding] Baha 6 Max SP and Baha 5 SP
- Thresholds audiology, sound-field [0.25, 0.5, 1.0, 2.0, 3.0, 4.0, 6.0, 8.0 9.0 and 10.0 kHz]

- Speech in quiet [% correctly perceived words at 65dB SPL]
- Evaluation of sound quality and listening effort through sound clips. Only Baha 6 Max SP and Baha 5 SP.

9.3 Hypotheses

9.3.1 Primary Hypothesis

The first primary efficacy analysis is the comparison regarding adaptive speech in noise [signal-to-noise ratio, 50% speech understanding] between Baha 6 Max SP and unaided using a two-sided Fisher's non-parametric permutation test for paired observations on significance level 0.005.

$$H_0: \mu_{\text{Baha 6 Max SP}} = \mu_{\text{unaided}}$$

$$H_1: \mu_{\text{Baha 6 Max SP}} > \mu_{\text{unaided}} \text{ or } \mu_{\text{Baha 6 SP}} < \mu_{\text{unaided}}$$

The second primary efficacy analysis is the comparison regarding preference of device between Baha 6 Max SP and unaided using a two-sided Sign test on significance level 0.045.

H_0 : Probability preference of Baha 6 Max SP before Baha 5 SP = 0.5, given preferred any.

H_1 : Probability preference of Baha 6 Max SP before Baha 5 SP > 0.5, given preferred any or Probability preference of Baha 6 Max SP before Baha 5 SP < 0.5, given preferred any.

9.4 Sample Size Determination

First primary analysis: Baha 6 Max SP vs unaided regard Adaptive speech in noise

Assuming an individual mean difference (aided Baha 6 Max SP minus unaided) in speech recognition in noise of 16 dB SNR with a standard deviation (SD) of 12.5 (Busch et al, 2015), a total sample of 15 eligible subjects are required to provide 90% power to reject the null hypothesis for the statistical test for the primary objective (change in dB SNR) using a two sided, alpha 0.005, with Two-sided Fisher's non-parametric permutation test for paired observations. As this is an internal Cochlear investigation, patients will be recruited until the number of required patients are obtained. Hence, no dropouts are expected (8).

Second primary analysis: Baha 6 Max SP vs Baha 5 SP regarding preference of device.

Assuming that 86% prefer Baha 6 Max SP, then 16 subjects are needed for 80% power with two-sided Sign test on significance level 0.045.

In order to satisfy both sample sizes for the primary analyses 16 subjects will be randomised into the investigation.

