6 OBJECTIVES AND ENDPOINTS

Primary Objectives	Primary Endpoints

To compare hearing performance of speech in noise between Baha 6 Max SP and the unaided hearing (superiority).
 
To compare the preference of device between Baha 6 Max SP and Baha 5 SP
	
Adaptive speech in noise [signal-to-noise ratio, 50% speech understanding]
 
Preference of device

Secondary Objectives	Secondary Endpoints

To compare hearing performance between Baha 6 Max SP and Baha 5 SP in a home/normal environment hearing environment
	
 • Diary 
 ◦ Daily use of the SP (hours) ◦ Change of battery ◦ Switch to their own SP and reason for change

To compare hearing performance between Baha 6 Max SP and Baha 5 SP.
	
 • Adaptive speech in noise [signal-to-noise ratio, 50% speech understanding] • Thresholds audiology, sound-field [0.25, 0.5, 1.0, 2.0, 3.0, 4.0, 6.0, 8.0, 9.0 and 10.0 kHz] • Speech in quiet [% correctly perceived words at 65dB SPL] • Evaluation of sound quality and listening effort through sound clips

To compare hearing performance between Baha 6 Max SP and unaided.
	
 • Thresholds audiology, sound-field [0.25, 0.5, 1.0, 2.0, 3.0, 4.0, 6.0 and 8.0 kHz] • Speech in quiet [% correctly perceived words at 65dB SPL]
Safety Objective	Safety Outcome measures
Adverse events (AEs)	Information will be collected from Visit 1 and onwards.
Device deficiency (DDs)	Information will be collected from Visit 1 and onwards.

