7.3.3 Adaptive Speech recognition in noise (Matrix test)

The purpose of this test is to establish the test subject's ability to recognise speech in the presence of background noise. The adaptive speech test in noise shall be conducted using validated lists of phonetically balanced sentences, with speech presented in sound-field from the front (0 degrees azimuth) and noise will also be presented from the front (figure 4). The noise shall be kept constant at 65 dB SPL, and the speech shall be adapted stepwise according to the software used to establish the speech-to-noise ratio (SNR) providing a 50% level of understanding.

Software and speech material to be used is the Matrix test in language specific versions as applicable.

The test shall be performed with the non-test ear blocked (in case of normal or near-normal hearing or a large asymmetry with the non-test ear having significantly better hearing thresholds).

The speakers should be at the height of the test subjects head and more than 1 metre away from the test subject. There should preferably be more than 1 metre of free space around the test subject in all directions. This is in accordance with the current standard.

FRONT

Figure 5: Speech in noise speaker position

At Visit 1 and 2, the speech in noise test will be performed for the aided situation with Baha 6 Max SP or Baha 5 SP depending on the randomisation order.

At visit 3 the test will be performed unaided.

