4.2 Analyses

4.2.1 Pass/Fail Criteria

If the signal-to-noise-ratio for a subject is at least 50% regarding speech understanding the subject will be classified as a responder. The primary objective of the study is that the null-hypothesis that the proportion of responders for the Baha 6 Max SP and the Baha 5 SP are equal.

If the two-sided p-value when testing the hypothesis above is below 5% the results of the study are considered successful.

This means that the pass/fail criteria for each subject is speech understanding and the pass-criteria is that the signal-to-noise-ratio for a subject is at least 50%.

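### SAP 4.2.1 declares success on a two-sided p-value with no condition on direction; separately, the planned SNR contrast in Protocol 9.4 carries the wrong sign

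*Protocol*

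**What the plan says.** **Objective.** Protocol section 6 sets the first primary comparison "between Baha 6 Max SP and the unaided hearing (superiority"). The second primary is device preference, Baha 6 Max against Baha 5.

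**Measurement.** Protocol 7.3.3 holds the noise at 65 dB SPL and moves the speech level to "establish the speech-to-noise ratio (SNR) providing a 50% level of understanding".

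**Planned effect.** Protocol 9.4, repeated in SAP 4.1, plans on: "Assuming an individual mean difference (aided Baha 6 Max SP minus unaided) in speech recognition in noise of 16 dB SNR". The SD taken for this difference is 12.5. The section concludes that "a total sample of 15 eligible subjects are required to provide 90% power to reject the null hypothesis"; the test it names for this is two-sided at alpha 0.005, a paired Fisher permutation test.

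**Protocol tests.** Section 9.3.1 states two-sided alternatives for both primaries, at 0.005 and 0.045. Section 9.6 reports the mean difference with a 99.5% interval and the proportion preferring Baha 6 Max with an exact interval. It also allows the remaining primary to be retested at 5% when the other is significant.

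**SAP success rule.** SAP 4.2.1 classes a subject as a responder when the SNR reaches 50% or more, and takes as null hypothesis that responder proportions are equal for Baha 6 Max and Baha 5. It then says: "If the two-sided p-value when testing the hypothesis above is below 5% the results of the study are considered successful". Neither 4.2.1 nor 4.2.2 asks that the difference favour Baha 6 Max.

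**The concern.** There are two separate defects, on two different comparisons.

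The first is the decision rule. The Protocol calls the study pivotal and gives regulatory approval as a main purpose. SAP 4.2.1 is the only place in either document that equates a p-value with success, and it does so without regard to direction. A significant result in favour of Baha 5 would satisfy the sentence as written.

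The second is the sign of the planned contrast against unaided hearing. The order of subtraction is explicit and the value is positive, but on this scale a benefit is negative. No sentence in either document says that lower SNR is better. Someone who took the planning statement as the definition of the estimate could therefore misread the sign of the reported mean difference.

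**Working it through.** **1. Direction of the scale.** Let L be the speech level at which a subject understands 50%. With noise fixed at 65 dB SPL, SNR = L − 65. Better hearing means a smaller L, hence a lower SNR. For one subject:

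aided − unaided = (L_aided − 65) − (L_unaided − 65) = L_aided − L_unaided.

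A value of +16 dB says the aided subject needs speech 16 dB louder than with no device. The intended benefit is −16 dB on this contrast, or +16 dB on unaided minus aided. This follows from the procedure in 7.3.3.

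**2. The plan's own sample size.** The inputs from 9.4 are a difference of 16, an SD of 12.5, two-sided alpha 0.005 and 90% power. The standardised difference is d = 16/12.5 = 1.28. Power of the paired t-test comes from the noncentral t distribution with n − 1 degrees of freedom and noncentrality 1.28·√n:

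| n | Power |
|---|---|
| 13 | 84.9% |
| 14 | 89.2% |
| 15 | 92.4% |
| 16 | 94.7% |

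The smallest n with at least 90% is 15, as stated. Simulating the exact sign-flip permutation test with normal differences, 1,000 runs per n, gave about 88% at n = 14 and 93% at n = 15.

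**3. Effect of correcting the sign.** With −16 dB the noncentrality changes sign and the two-sided test is symmetric. At n = 15, power is again 92.4% (simulation 92.4%), now in the lower tail. N stays at 15.

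**4. Effect of adding a direction condition to the Protocol's test.** If the true effect is −16 dB, requiring aided below unaided as well as two-sided p < 0.005 leaves power at 92.4%. If +16 dB were literally true, significance alone would occur with probability 92.4%, and significance with aided below unaided with probability about 2.5 × 10⁻¹³. The condition costs nothing when the device works and excludes the adverse result when it does not.

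**5. The SAP 4.2.1 rule, read in turn.**
- As a percentage cut-off on SNR, it cannot be applied, because SNR here is in dB.
- As a threshold on the SNR value itself, a requirement of at least some value selects the unfavourable end of the scale.
- As 50% speech understanding, the adaptive procedure targets that level for every subject in every condition. All subjects would be responders with both devices, no pairs would be discordant, and the test could not reject in either direction.

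The missing direction therefore matters for any workable version of the rule, and the criterion itself must be replaced.

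**6. Illustration of a direction-free rule.** The documents give no responder rates, so the rule in 4.2.1 cannot be quantified directly. Assume instead an exact binomial test with 16 informative pairs, or equally 16 stated preferences. The lower tail at 3 or fewer is (1 + 16 + 120 + 560)/2¹⁶ = 697/65,536 = 0.0106, so two-sided p = 0.021 at 3 of 16 and, by symmetry, at 13 of 16. At 12 of 16, p = 0.077. Rejection at 5% thus occurs at 13 or more, or at 3 or fewer. If the true share favouring Baha 6 Max were 0.40, a rejection against it would occur with probability 6.5%; if 0.14, with probability 82.4%. These figures show how such a rule behaves. They do not measure the responder rule.

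**The case against.** Several points on the other side are sound.

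- **The sign may be only notation.** The 16 dB could be meant as an unsigned size, and it changes neither N nor power. That stands, so this part is a correction of sign and no more. It still needs making, because the order of subtraction is written out and the SAP repeats it.
- **The two defects do not depend on each other.** A reader might infer that the reversed sign is what lets an adverse result pass. The documents do not support this. The sign concerns mean SNR against unaided hearing; the success sentence concerns responder proportions against Baha 5. The consequence for success comes from SAP 4.2.1 alone.
- **Two-sided hypotheses are not a fault.** A reader might infer that 9.3.1 contradicts a superiority objective. It does not. A two-sided test with a favourable estimate is an ordinary way to show superiority. The Protocol nowhere says that significance alone is success, and the estimates and intervals in 9.6 will show direction.
- **The scale is not undeterminable.** A reader might infer that the favourable sign cannot be worked out at all. The procedure in 7.3.3 settles it; what is missing is a sentence saying so.
- **The responder test may be unable to reject.** Under the third reading in step 5 of the working, an adverse success could not arise. That limits the practical claim, but it replaces one defect with another and does not rescue the rule.

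**Conclusion.** Wrong as written, and cheap to correct relative to what depends on it. SAP 4.2.1 would label a significant result favouring the comparator a success. This rests on the literal text and on a responder measure that can differ between devices. The criterion given is not interpretable in dB, so the probability of an adverse success under that rule cannot be stated from the documents. The 13-of-16 and 3-of-16 counts (p = 0.021 each, if all 16 state a preference) are illustration only, since 4.2.1 is not written for preference.

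The sign in Protocol 9.4 and SAP 4.1 is a separate and smaller error. It rests on the scale direction implied by 7.3.3. The planned N of 15 is reproduced, with power of about 92% under either sign. Nothing here supports a claim that the sample size is wrong or that the two-sided hypotheses should be changed.

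**What to change.** 1. In Protocol 9.4 and SAP 4.1, write the planned effect as unaided minus aided Baha 6 Max = 16 dB SNR, and add that lower SNR is better.

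2. Replace the success rule in SAP 4.2.1 with one tied to the Protocol's primary comparisons:
   - The first objective is met only if the two-sided paired permutation p-value is below its allocated level and mean SNR is lower with Baha 6 Max than unaided.
   - The second objective is met only if the two-sided sign test p-value is below its allocated level and more than half of stated preferences are for Baha 6 Max.

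   The allocated levels are 0.005 and 0.045, with the 5% retest that Protocol 9.6 allows.

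3. Remove the responder criterion from SAP 4.2.1 and 4.2.2, and restore the Protocol's endpoint, comparator and test there.

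The two-sided hypotheses in Protocol 9.3.1 can stay.

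**Cost.** The Protocol change is wording only; test, alpha and sample size are untouched. The SAP change is more than wording, because 4.2.1 and 4.2.2 currently name a different endpoint, comparator and test for the first primary and have to be rewritten to match the Protocol. No new data or further subjects are needed.

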9 STATISTICAL CONSIDERATIONS

9.1 General Statistical Considerations

The investigation will have two primary analyses, one regarding Adaptive speech in noise between Baha 6 Max SP and unaided hearing ($\alpha = 0.005$) and one regarding preference between Baha 6 Max SP and Baha 5 SP ($\alpha = 0.045$). These endpoints will be evaluated using the decision rules of the Holm's test. (Ref NEJM2). With these procedures we will have a total type I error <0.05 .

For the comparison between the Baha 6 Max SP and unaided the design don't take care of period effect so the statistical analyses will be paired. For the comparison between Baha 6 Max SP and Baha 5 SP a cross over design was applied and the statistical analyses will be adjusted for period effect.

The main results for all outcome variables are the estimate of mean differences with 95% confidence interval (CI) with a descriptive p-value. The p-value will only have a confirmatory value for the two primary analyses.

For comparison between the Baha 6 Max SP and unaided Fisher's non-parametric permutation test for paired observations will be used for continuous variables and Sign test for dichotomous variables and ordered categorical variables.

For the comparison between Baha 6 Max SP and Baha 5 SP the following period adjusted analysis should be performed for continuous variables: For each subject take the difference between the measurement in second period and the measurement in first period. Then analyse these differences between the subjects randomised to Baha 6 Max SP in the first period and the subjects randomised to Baha 5 SP in the first period with Fisher's two-sided non-parametric permutation test. The Fisher's permutation test is preferable because it is non-parametric and gives consistent 95% CI.

For the comparison between Baha 6 Max SP and Baha 5 SP the following period adjusted analysis should be performed for dichotomous and ordered categorical variables: For each subject take the difference as, improved no change and worsened, between the measurement in second period and the measurement in first period. Then analyse these ordered categorical differences between the subjects randomised to Baha 6 Max SP in the first period and the subjects randomised to Baha 5 SP in the first period with Mantel-Haenszel chi-square test.

For comparison of preference of device between Baha 6 Max SP and Baha 5 SP the Sign test will be used.

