9.6 Primary Endpoint Analyses

The first primary endpoint analysis will be the comparison of adaptive speech in noise [signal-to-noise ratio, 50% speech understanding] between the Baha 6 Max SP and unaided with two-sided Fisher's non-parametric permutation test for paired observations on significance level 0.005 on the FAS population. Mean difference with 99.5% confidence interval will be given together with the distribution of the difference.

The second primary endpoint analysis will be the comparison between Baha 6 Max SP and Baha 5 SP regarding preference of device with two-sided Sign test on significance level. Proportion of preferences for Baha 6 Max SP with exact 95 % CI will be calculated.

If one of the two primary efficacy analyses are significant but not the other, the other can be retested at the 5% significance level according to the decision rule of the Holms test (9).

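### Minor, free improvement: the sign test on preference cannot use the last part of its 0.045, so the first primary's initial level could be 0.01 instead of 0.005 at no cost

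*Protocol*

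**What the plan says.** Protocol Section 9.1 names two primary analyses, allots them 0.005 and 0.045, and claims: "With these procedures we will have a total type I error <0.05". Under Section 9.3.1 the first primary is tested "using a two-sided Fisher's non-parametric permutation test for paired observations on significance level 0.005". The null hypothesis for preference is "Probability preference of Baha 6 Max SP before Baha 5 SP = 0.5, given preferred any", so subjects without a preference drop out and the effective number can fall below 16.

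Section 9.4 plans the first primary on a mean paired difference "in speech recognition in noise of 16 dB SNR with a standard deviation (SD) of 12.5", needing 15 subjects for 90% power. For preference it says: "Assuming that 86% prefer Baha 6 Max SP, then 16 subjects are needed for 80% power with two-sided Sign test on significance level 0.045". Sixteen subjects are to be randomised.

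Section 9.6 adds that if one primary succeeds and the other does not, "the other can be retested at the 5% significance level according to the decision rule of the Holms test". It gives a 99.5% confidence interval for the first primary and leaves the level for the preference test blank.

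The SAP repeats 0.0050 in its sample-size text (4.1). Sections 4.2.1 and 4.2.2 give a single 5% success criterion, with no split and no Holm rule, and compare Baha 6 Max with Baha 5 in the first primary.

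**The concern.** An exact test with few observations has only a few possible p-values. Any nominal level between two neighbouring p-values gives the same test, and the excess is wasted. Here 90% of the total alpha (0.045 of 0.05) goes to such a test. The comparison with unaided hearing, which Section 7.1.1 ties to regulatory approval, starts at 0.005. If part of the 0.045 can never be used, the first primary is held to a stricter initial level than error control requires. The cost would be felt when preference fails, because the Holm retest then does not rescue the first primary, and when subjects are lost. Losses are possible: withdrawn subjects are not replaced (7.2.6), nothing is imputed (9.1), and unaided testing takes place only at Visit 3 (7.3.3).

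**Working it through.** **Inputs.** From Protocol 9.1, 9.3.1, 9.4 and 9.6: levels 0.005 and 0.045; 16 subjects; 86% preference; mean difference 16 dB, SD 12.5; Holm retest at 0.05. Added assumptions: paired t as a stand-in for the permutation test, independent endpoints, and, for one sensitivity check, 70% preference.

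**1. The plan's own figures.** Preference, n = 16: rejecting at 13 or more (or 3 or fewer) has two-sided size 2 × (560 + 120 + 16 + 1)/65,536 = 0.0213. Power at 86% is 82.4%, which meets the stated 80%. First primary: standardised effect 16/12.5 = 1.28, noncentrality 1.28 × √n, n − 1 degrees of freedom. At 0.005 the smallest n with 90% power is 15 (92.4%; a simulated permutation test gives about 91%). Both stated sizes reproduce.

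**2. Attainable levels of the sign test.** At n = 16 the next step, 12 or more, has size 2 × 2,517/65,536 = 0.0768. The largest two-sided p-value not above 0.05, by number of stated preferences, is:

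| Preferences | Reject at | Size |
|---|---|---|
| 6 | 6 | 0.0313 |
| 7 | 7 | 0.0156 |
| 8 | 8 | 0.0078 |
| 9 | 8 | 0.0391 |
| 10 | 9 | 0.0215 |
| 11 | 10 | 0.0117 |
| 12 | 10 | 0.0386 |
| 13 | 11 | 0.0225 |
| 14 | 12 | 0.0129 |
| 15 | 12 | 0.0352 |
| 16 | 13 | 0.0213 |

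With five or fewer preferences the test cannot reject. The largest entry is 0.0391, at 9 preferences: 2 × (9 + 1)/512. The cut-offs are therefore identical at 0.04, 0.045 and 0.05. A value between 0.045 and 0.05 first appears at 17 preferences (0.0490), beyond the planned number.

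**3. What can be moved.** Whatever the number of ties, the first primary can have 0.05 − 0.0391 = 0.0109, so 0.01 is safe. If all 16 were certain to state a preference, it could have 0.05 − 0.0213 = 0.0287. That level is not safe in advance: with one tie the sum would be 0.0287 + 0.0352 = 0.0639.

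Under 0.01/0.04, if both nulls are true the error is at most 0.01 + 0.0391 = 0.0491. If only one null is true, it is tested at no more than 0.05. Family-wise error stays within 0.05.

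**4. First-step power of the first primary (paired t).**

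| n | 0.005 | 0.01 |
|---|---|---|
| 16 | 94.7% | 97.5% |
| 15 | 92.4% | 96.2% |
| 14 | 89.2% | 94.3% |
| 13 | 84.9% | 91.6% |

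**5. Overall power with the retest.** With s the probability that preference succeeds and π(α) the power at level α, overall power = s × π(0.05) + (1 − s) × π(α₁).

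- n = 16, 86% preference, s = 0.8237: 0.8237 × 0.9975 + 0.1763 × 0.9470 = 98.9%. With α₁ = 0.01 it is 99.3%.
- n = 14 (14 preferences), s = 0.6889: 0.6889 × 0.9929 + 0.3111 × 0.8918 = 96.1%. With 0.01 it is 97.7%.
- 70% preference (assumed): 95.9% to 98.0% at n = 16, and 90.8% to 95.1% at n = 14.

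**The case against.** The strongest reply is that nothing in the protocol's split is wrong. It is prespecified, it controls the error, discreteness makes it conservative and not invalid, and 16 subjects give more than the 90% planned for the first primary. That stands.

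Three stronger readings are tempting, and the documents do not support them.

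- A reader might infer from step 4 that the present split loses 90% power at 14 subjects. That is true of the first step alone. Section 9.6 retests the first primary at 5% when preference succeeds, and under the plan's assumptions overall power at 14 is 96.1%. It drops below 90% there only if preference nearly always fails (89.3% at a true preference of 50%).
- A reader might add 0.005 + 0.0213 and conclude that the scheme spends only 0.026 of its 0.05. That holds only if both nulls are true and all 16 state a preference. If 86% truly prefer Baha 6 Max, the first primary's error is about 0.8237 × 0.05 + 0.1763 × 0.005 = 0.042.
- A reader might claim that 0.005 could be raised nearly sixfold, to 0.0287. That requires all 16 to state a preference, while the hypothesis in 9.3.1 allows ties.

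It is also fair that 13 or 14 analysable subjects lies outside the plan: Section 9.4 expects no dropouts, and 9.1 continues the study until enough subjects are available. The bar on replacement in 7.2.6 weakens that assurance but does not make losses likely.

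**Conclusion.** This is a small inefficiency, not an error. Between 0.0391 and 0.05 the preference test gains nothing from a higher level, so doubling the first primary's initial level to 0.01 is free for any number of ties. That part is exact and rests only on there being at most 16 preferences. The benefit depends on the assumptions: 2.8 points of first-step power at n = 16, about half a point once the retest is counted at 86% preference, and 2 to 4 points if preference is nearer 70% (2.1 at n = 16, 4.3 at n = 14). The power figures assume normal differences with the plan's mean and SD; the overall figures also assume independent endpoints. The stated sample sizes stand.

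**What to change.** Before any outcome data are examined, and by protocol amendment:

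- Replace 0.005/0.045 by 0.01/0.04 in 9.1, 9.3.1, 9.4 and 9.6, and enter the missing preference level in 9.6.
- Change the first primary's interval from 99.5% to 99%.
- Keep the Holm retest at 5%.
- State the preference cut-offs: 13 of 16, 12 of 15, 12 of 14, 11 of 13, 10 of 12.
- Update the level in SAP 4.1. Put the same split and Holm rule into SAP 4.2.1 and 4.2.2 when these are reconciled with the protocol. That reconciliation comes first: under the SAP's single 5% criterion the split is not applied at all.

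The change costs no subjects, no preference power and no type I error. It does need an amendment with ethics committee notification (Section 18), and written approval if it is substantial (Section 16). The study is open label and run by sponsor staff, and the integrated SAP is dated March 2021, so the sponsor should document that no outcome data had been seen. If that cannot be shown, keep 0.005/0.045 and report the level that the sign test actually attained.
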